10 THE QUINTENT RECRUITMENT INTERVENTION (QRI) - "THE INFORMATION STUDY"

The Quintet Recruitment Intervention ("Information Study") will be led by researchers at the University of Bristol and will be undertaken in two iterative stages as detailed below. The objectives of the QRI are detailed in Table 1.

Objectives	Outcome Measures	Time point(s)
To understand the recruitment process in the PART study (Internal Pilot Phase I)	 The QRI team will present a summary of anonymised findings emerging from the QRI, based upon: 1. Analysis of interviews and audio recordings with the TMG, recruiters and potential participants for PART. 2. Results from the mapping of recruitment processes at PART study sites. 	Depending on the rate of data collection, it is anticipated that preliminary findings will be obtained within the first three to six months of recruitment.

Table 1: QRI study objectives and outcome measures

	 Review of information given to the participant in information sheets and through the recording of informed consent discussions. 	
To develop strategies to optimise recruitment and informed consent (Phase II)	Suggestions will be made to change aspects of design, conduct, or training.	Phase II will continue for the duration of recruitment until the target of 800 men is reached.

10.1 QRI PHASE I: Understanding recruitment

The aim of the first phase of the QRI is to understand the process for recruiting patients into the PART study and how this is conducted in the recruiting sites taking part in the study. A multi-faced, flexible approach will be used to investigate site-specific or wider recruitment obstacles.

The following research methods will be used in this phase of the QRI:

1) Interviews with all parties involved in recruitment into the study.

Semi-structured interviews will be undertaken with three groups:

- 1) Members of the Trial Management Group (TMG) and the Study Office
- 2) Members of the research team involved in study recruitment at participating sites
- 3) Potentially eligible participants who have been approached about the study at participating sites

Interviews with members of the TMG and members of the research team at participating sites will explore their perspectives on PART, and experiences of recruitment. Key topics that will be explored will include perspectives on the study design and protocol; views about the evidence on which the trial is based; perceptions of uncertainty/equipoise in relation to the RCT treatment arms; views about how the treatment arms and protocol are delivered in their clinical centre; methods for identifying eligible patients; views on eligibility; and examples of actual recruitment successes and difficulties.

Interviews with patients approached about the study at participating sites will explore views on the presentation of study information, understandings of study processes (e.g. randomisation), and reasons underlying decisions to accept or decline the study. Patients will be purposefully sampled for maximum variation based on age, study centre, and the final decision about trial participation (i.e. accept or decline), and treatment selected.

Interviewees will be contacted by a researcher from the University of Bristol if they have consented to this part of the Information Study. Interviews will be arranged for a time and place convenient to the interviewee and may be in person or using other remote means of communication (whichever is preferable).

A purposeful sampling strategy will also be used to ensure that views of PART and recruitment are captured from a range of health care professional's perspectives. This will include sampling by professional role (e.g. surgeons, research nurses) and recruitment site, and recruitment rate (i.e. high to low recruitment). RCT participant characteristics will be assessed as the study progresses, and individuals or groups that were under-represented will be targeted. It is anticipated that approximately 20 healthcare professionals and 20 participants will be interviewed, although the

number of participants will ultimately be guided by saturation (whereby data collection continues until no new themes are emerging).

2) Audio-recording discussions between the site research team and patients about study participation

Consent will be sought from potential study participants to record any discussions they have with the local site research team regarding them taking part in the study before full study information is given to them. Following appropriate consent, scheduled appointments during which the study is discussed will be audio-recorded. This will also include any follow-up telephone conversations. The audio recordings will be used to explore information provision, recruitment techniques, management of participant treatment preferences, and randomisation discussions, to identify recruitment difficulties and improve information provision. An encrypted audio recording device for recording recruitment discussions will be supplied by the researchers at the University of Bristol.

3) Mapping of eligibility and recruitment pathways

Detailed eligibility and recruitment pathways will be compiled for participating sites, noting the point at which patients receive information about the study, which members of the clinical team they meet, and the timing and frequency of appointments. The QRI researcher will also work closely with the PART study office to review logs of potential participants as they proceed through screening and eligibility phases, to help identify points at which patients do not continue with recruitment to PART. Logs of eligible and recruited patients will be assembled using simple flow charts and counts to display numbers and percentages of patients for each stage of the eligibility and recruitment processes. These figures will be compared across sites and considered in relation to estimates. The screening log data used during this process is not identifiable.

4) Observation of TMG and Investigator Meetings

The QRI researcher will regularly observe TMG meetings (which may be conducted remotely or in person) to gain an overview of trial conduct and overarching challenges (logistical issues, etc.). Observation of these meetings can elucidate new lines of enquiry and add new dimensions to challenges that have emerged through other data collection methods.

10.2 QRI PHASE 2: Feedback and implementation of strategies to improve recruitment

The QRI research team will present summaries of anonymised findings to the CI and the Trial Management Group, identifying the factors that appear to be hindering recruitment with supporting evidence. The QRI team will then suggest a potential plan of action to improve recruitment, based on the findings from the QRI Phase 1, the PART QRI Feasibility Study, and experience from other RCTs for generic issues. The aspects that the QRI team will be able to work on with the PART study team are likely to include: providing feedback and training on generic recruitment issues, such as how to present the study design more clearly to improve levels of understanding during appointments; how to approach patients' treatment preferences; and facilitating discussions around issues of clinical pathways and eligibility assessment, equipoise, and team-working. The responsibility for deciding on the details of the plan of action and implementing changes and facilitating the QRI team's work will lie with the CI.

10.3 QRI Inclusion Criteria

- Patients approached for participation in the PART study
- Healthcare professionals involved in management, operation or recruitment for the PART study

10.4 QRI Exclusion Criteria

- Patients who do not wish to have consultations recorded and/or participate in interview
- Healthcare professionals who do not wish to have consultations recorded and/or participate in interview.

11 PARTICIPANT ELIGIBILITY CRITERIA

11.1 Timing of eligibility assessment

Eligibility will be assessed upon initial entry into the study and checked at the point of randomisation. Following randomisation, study treatment will be planned as per the randomised allocation. Participants will be placed on NHS waiting lists for the study intervention in accordance with usual NHS policies. All study participants will be assessed immediately prior to receiving the study intervention as per standard of care prior to any procedure/treatment within the NHS, and any participants found to be unsuitable for the planned study intervention at this point will be withdrawn from the study.

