8.5 Definition of primary treatment failure

Primary treatment failure will be determined by repeat prostate biopsies (either as part of the routine protocol-defined time point), or "for cause", or clinical appearance of symptoms demonstrating disease progression, or radiological concerns on repeat imaging, or due to clinical concern. Primary treatment failure is defined according to the treatment received:

Treatment Arm	Treatment received within arm	Definition of primary treatment failure	
Partial Ablation	HIFU or IRE	 Any of the following: a) persistent intermediate-risk PCa in a treated area after one repeat PA treatment b) repeat PA treatment requiring more than 75% of the prostate to be treated, and/or indication for radical treatment c) positive biopsies demonstrating high-risk PCa (Gleason Grade Group 4-5) at any time d) extra-prostatic disease progression defined by imaging, clinical examination, or biopsy findings e) the development of systemic disease requiring long-term androgen deprivation therapy 	
Radical Treatment	Radical prostatectomy (RP)	 Any of the following: a) a rising serum PSA reaching ≥0.2 ng/ml following initial reduction to <0.1 ng/ml after surgery b) a failure of serum PSA to fall below 0.1 ng/ml after surgery c) clinical progression to local recurrence/systemic disease d) the need for long-term androgen deprivation therapy 	
	Radical radiotherapy (RRT) or low dose- rate brachytherapy (LDR-B)	 Defined using the RTOG-ASTRO Phoenix criteria (48) as: a) a rise of post-treatment PSA ≥2.0 ng/ml above the post-treatment nadir or b) clinical progression to systemic disease with the need for long-term androgen deprivation therapy 	

Further information regarding diagnosis and management of primary treatment failure can be found in section 16.4.

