16.8 Withdrawal

Withdrawal of consent means that a participant has expressed a wish to withdraw from the study altogether, or from certain aspects of the study only. The type of withdrawal will be collected on the CRF labelled 'Withdrawal'.

Participants may also be withdrawn from the study (or aspects of the study) by their clinician if they believe the participant needs to be withdrawn.

PART_Protocol_V3.0_15May2024_Clean.docx Page **49** of **77**

The Withdrawal CRF should be completed to document the reasons for withdrawal, and state who made the decision to withdraw. Discussions and decisions regarding withdrawal should be documented in the participant's medical notes. Investigators should continue to follow-up any SAEs and should continue to report any SAEs to resolution in the CRF in accordance with the safety reporting section.

Where a participant expresses a wish to withdraw from the study, the study team will determine which aspect(s) of the study the participant wishes to withdraw from; all other aspects of the study/follow-up will be continued.

The aspects of the study that the participant may request to withdraw from are as follows:

- No longer willing to receive study intervention
- No longer willing to complete study questionnaires
 - This refers to the health-related quality of life questionnaires and health care use questionnaires sent directly to participants by the study office
- No longer willing to take part in qualitative aspects of study
 - This refers to the interview for the QuinteT Recruitment Intervention/ the "Information Study"
- No longer willing to provide study tissue samples
 - This refers to any follow-up biopsies
- No longer willing to have study MRIs
- No longer willing to attend study visits
- No longer willing to be contacted by the research team to obtain CRF/outcome data
- No longer willing to have standard of care data from the medical record provided to the study
- No longer willing for standard of care data from Health data providers e.g. NHS digital, to be provided to the study

Where a participant wishes to withdraw from all aspects of study participation detailed above, this will be recorded on the Withdrawal CRF as full withdrawal.

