Completion of the Withdrawal CRF will trigger a notification to the Study Office. Appropriate action will be taken by the study teams (centrally at the study office and by the local research team at each participating site) to ensure compliance with the participant's withdrawal request. This may include marking future CRFs as not applicable and ensuring any relevant communications which the participant had consented to receive regarding their participation are no longer sent.

Data collected up to the point of withdrawal will be used in the study analysis.

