19.4 Description of Statistical Methods

The primary analysis will be performed according to the Intention-To-Treat principle. Treatment failure will be compared between radical treatment and PA treatment using survival analysis techniques. Statistical significance between treatment groups will be assessed using log rank methods, and Kaplan-Meier survival curves will be used for graphical representation. Patients without treatment failure will be censored at time of death or time of last follow-up. Additional supporting analyses will be undertaken using Cox proportional hazards regression models adjusting for stratification factors and time from randomisation to start of treatment. Patients without treatment failure will be censored at their last known treatment failure free time.

For PORPUS and the other disease-specific HRQoL outcomes, Mixed Models for Repeated Measures (MMRM) will be used to evaluate differences over time by treatment group. MMRM models will be adjusted for treatment, baseline score, stratification factors, visit and a treatment by visit interaction as fixed effect terms, with patient included as a random effect. Differences between treatment groups will be reported as mean difference with 95% confidence intervals. Absolute and percentage average changes in HRQoL outcomes from baseline assessment will be displayed graphically. HRQoL forms that are returned partially complete will be analysed according to the scoring instructions for each questionnaire. The MMRM analyses will minimise the impact of missing data so the use of multiple imputation or other methods for dealing with missing data is not planned. Survival analysis techniques, as described for the treatment failure primary outcome, will also be used to compare differences between radical treatment and PA treatment for time to disease progression (including metastases), time to disease-specific mortality, and time to all-cause mortality. Patients without

disease progression at time of analysis will be censored at time of death or time of last known alive date.

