19.5 Inclusion in analysis

All analyses will be on an intention-to-treat basis. This means that patients will be analysed as they are randomised irrespective of the treatment actually received. The intention-to-treat population will include all patients who have given their informed consent and for whom there is confirmation of successful allocation of a randomisation number.

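### Section 11.1 withdraws from the study, not just from the intervention, randomised men found unsuitable before treatment, so outcomes that intention-to-treat needs are lost

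*Protocol*

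**What the plan says.** Section 11.1 places an assessment after randomisation and immediately before the intervention, for participants in both arms, and states that "any participants found to be unsuitable for the planned study intervention at this point will be withdrawn from the study". The synopsis (section 6) allows up to 12 months between randomisation and the start of treatment.

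Section 19.5 defines the analysis set broadly: "The intention-to-treat population will include all patients who have given their informed consent" and have a confirmed randomisation number. It adds that "patients will be analysed as they are randomised irrespective of the treatment actually received".

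Section 16.8 governs withdrawal. When a participant asks to withdraw from one aspect, "all other aspects of the study/follow-up will be continued". Clinician-led withdrawal may be whole or partial: "Participants may also be withdrawn from the study (or aspects of the study) by their clinician". For withdrawn men, "Data collected up to the point of withdrawal will be used in the study analysis".

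Section 19.4 states: "Patients without treatment failure will be censored at time of death or time of last follow-up". Section 8.5 adds that "Primary treatment failure is defined according to the treatment received", and its table covers only men who received HIFU, IRE, prostatectomy, radiotherapy or brachytherapy.

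**The concern.** Analysing men as randomised requires outcomes from those who did not get the allocated treatment. Section 11.1 tells sites to end study participation for exactly those men, including any who would be willing to stay. Their failure status and PORPUS-P scores after that point are not collected, so both co-primary outcomes are affected.

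If leaving for this reason is related to outcome and differs by arm, the censoring is informative and randomisation no longer protects the comparison. A difference by arm is plausible from the protocol. PA has its own safety contraindications (11.5), while a man in the radical arm who is unsuitable for one option may be able to have another of the three (13.2.1). A statistical analysis plan cannot repair this, because it cannot recover data that sites were told to stop collecting.

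**Working it through.** **Following one man through the text.** He consents, is randomised and waits for treatment. At the pre-treatment check he is judged unsuitable for the planned intervention.

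1. 11.1: he is withdrawn from the study. The text offers no partial form.
2. 19.5: he remains in the intention-to-treat population, because no exclusion applies to him.
3. 16.8: only his data up to that date are used.
4. 19.4: without a recorded failure, he is censored at that date, before any treatment.
5. 8.5: had he been kept, none of the listed definitions would say how failure is judged if he receives none of the listed treatments.

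Steps 2 to 4 honour 19.5 in form but not in effect. Step 1 also conflicts with the partial withdrawal that 16.8 allows.

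**The plan's own figures.** The protocol gives no number of such men. The nearest figure is the power statement in 19.2: 10% v 20% failure, 800 men, 10% dropout, p<0.025, about 88%. The hazard ratio reproduces: log(0.9)/log(0.8) = 0.4722. With 720 evaluable men (360 per arm) and two-sided 0.025, standard formulas give 92.3% to 95.1%. About 88% can be reached under added or changed assumptions, such as reading the rates as 5-year rates with staggered entry. The document does not say which method was used, so the 88% is neither confirmed nor disputed here, and this point does not depend on it.

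**Illustration of the censoring effect.** Assumptions, none of which is in the documents except the 10% and 20% rates: withdrawals occur in the PA arm only, a share w of that arm is withdrawn before any failure is recorded, and their true failure risk is r. Then

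observed PA failure = (0.20 − w × r) / (1 − w).

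For w = 5% (0.05 × 400 = 20 men):

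| Risk r in withdrawn men | Calculation | Observed PA failure | Difference from 10% | Power |
|---|---|---|---|---|
| 10% | (0.20 − 0.005)/0.95 | 20.5% | 10.5 points | 95.1% |
| 20% | (0.20 − 0.010)/0.95 | 20.0% | 10.0 points | 93.1% |
| 40% | (0.20 − 0.020)/0.95 | 18.9% | 8.9 points | 87.3% |
| 60% | (0.20 − 0.030)/0.95 | 17.9% | 7.9 points | 78.4% |

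Power is for two proportions at two-sided 0.025, with 360 radical men and 0.95 × 360 = 342 PA men. The baseline on the same formula, without these withdrawals, is 93.7%.

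Varying w at r = 40%:
- w = 2%: (0.20 − 0.008)/0.98 = 19.6%, power 91.6%.
- w = 10%: (0.20 − 0.040)/0.90 = 17.8%, power 76.1%.

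If withdrawals are equal in both arms and unrelated to prognosis, there is no bias, and power runs from 93.2% (2% withdrawn) to 90.9% (10% withdrawn).

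No comparable calculation is made for PORPUS-P, because the documents give nothing on the scores of such men.

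**The case against.** The strongest reply is that the men are not excluded. Section 19.5 keeps all of them in the analysis set and 16.8 uses what they contributed. A man withdrawn late in the waiting period may already have given PORPUS-P scores at 3 and 6 months and some failure-free time. This stands. A reader might infer from 11.1 that these men are removed from the failure comparison, but the documents do not say so. The loss is of later follow-up.

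A reader might also infer that the withdrawn men have poor prognosis and leave mainly from the PA arm, flattering PA. The documents do not support that either:
- Section 11.1 describes the check as routine pre-procedure assessment and applies it to both arms.
- Table 3 schedules no mpMRI or biopsy between randomisation and treatment that would detect progression.
- Inclusion criterion 5 and exclusion criteria 3 and 4 screen every man for suitability for both approaches before randomisation.
- The PA planning team (9.5) recommends a modality. Nothing says that it withdraws anyone.

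Unsuitability may have nothing to do with the cancer. As the working shows, the bias is nil at average risk and reverses at lower risk.

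Finally, simply keeping these men in follow-up is not a complete remedy. Section 8.5 gives no failure definition for a man who receives no listed treatment, and sections 14.7 (loss of capacity) and 16.8 (clinician-led withdrawal) contain other grounds for withdrawal that must be respected. Both points stand and shape the fix.

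None of this removes the conflict. The rule stops collection of the very data that would show whether the censoring is harmless.

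**Conclusion.** Wrong as written. Section 11.1 requires whole withdrawal from the study where stopping the intervention would be enough. Read with 16.8 and 19.4, this loses the later failure and PORPUS-P outcomes of randomised men and is contrary in effect to 19.5.

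The conclusion rests on the text alone and needs no assumed figure. The size does need one. The documents give no rate, reason or prognosis, so the direction and magnitude of any bias are unknown. With 5% of the PA arm withdrawn and true PA failure of 20%, observed PA failure runs from 17.9% to 20.5% as the assumed risk in those men falls from 60% to 10%. That range illustrates sensitivity and does not predict what will happen. A claim that the rule favours PA, or that it costs a given amount of power, would go beyond the documents.

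**What to change.** Reconcile 11.1 with 16.8 and 19.5 by amendment:

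- **11.1:** a man who cannot have the planned intervention stops that intervention only. He remains in PSA, outcome, questionnaire and safety follow-up and is analysed in the arm to which he was randomised. This is subject to the existing provisions on consent and clinician-led withdrawal (16.8) and loss of capacity (14.7).
- **8.5:** state how primary treatment failure is determined for men who do not receive an allocated treatment.
- **Reporting:** give the number of men found unsuitable before treatment, with reasons, by arm.

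No change to any clinical suitability rule is proposed. The cost is a short amendment to two sections and continued follow-up of these men through data collection already in place. The change should be made early, because outcomes not collected in the meantime may not be recoverable.
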